2.1.2 Pleural infection aetiology

Although primary pleural infection (without any evidence of lung parenchymal involvement) is increasingly recognised as an important condition, (12) the majority of patients will present having suffered a pneumonic illness in the build-up to their presentation. Up to 60% of patients with pneumonia will go on to develop an associated reactive fluid collection (parapneumonic effusion) around the lung, and around 10% of these go on to develop evidence of secondary infection. (13-15) The diagnosis of pleural infection can be made directly, by the demonstration of pus (empyema) or organisms in a pleural sample, or indirectly, when markers of high metabolic activity (such as a low glucose or pH level) are found. Although not entirely specific, indirect these parameters are codified in national guidelines (1) and commonly form the basis of entry criteria to studies recruiting from the pleural infection population.

The pattern of organisms implicated in pleural infection has evolved over the last few decades, with the most significant shift assumed to be associated with the widespread introduction of antibiotics. (13) Gram positive cocci, specifically the *Streptococcus anginosus* group in adults and *Strep pneumoniae* in children, are the primary culprits in community-acquired disease, although Gram-negatives (e.g. *Haemophilus influenzae*) and anaerobes are also found not infrequently. (16) Given this information, the choice of appropriate empirical antibiotics in pleural infection often differs subtly from that required in pneumonia. (1) Modern nucleic acid amplification techniques (NAAT) are beginning to reveal more about the pleural infection microbiome, suggesting a complexity and individuality which is not readily apparent using traditional culture and microscopy. (17) NAAT, however, is not yet in widespread clinical use and thus remains a tool largely reserved for research. The distinction between community-acquired disease and the less common healthcare-associated pleural infection, HAPI, (which accounts for around 15% of cases (12)) is an important one to make in deciding initial treatment. HAPI carries a significantly higher chance of morbidity and mortality and is caused by a different spectrum of bacteria, largely *Staphylococci* including MRSA, necessitating alternative antibiotic approaches. (12)

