4.3 STUDY OUTCOME MEASURES

4.3.1 Primary outcome

The primary outcome is the feasibility of being able to recruit patients and randomise them to undergo medical thoracoscopy for pleural infection, and of being able to deliver the trial protocol. This will be assessed as follows:

- Pre-randomisation:
 - The total number of pre-screen and screen failures, and the proportions of each compared to the overall number assessed for trial involvement
- Post-randomisation:
 - The total number of allocation failures in both arms of the study

Pre-screen, screen and allocation failures are defined in sections 5.1 and 6.3.3.

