5.1.1 Pre-screening

All patients who have a suspected infected pleural effusion, based on radiological findings and routine clinical assessment by an appropriate specialist, should be entered onto the pre-screening log (“pre-screened” patients). All pre-screened patients should be assessed against the inclusion and exclusion criteria, detailed below. Those who are ineligible for trial entry should have the reasons for this entered on the log, and will be deemed to be “pre-screen failures”. Patients may be entered onto the pre-screening log retrospectively, but only if they presented with suspected pleural infection during the trial recruitment period.

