5.2 INCLUSION CRITERIA

1. Suspected pleural infection, defined as an effusion (in the appropriate clinical context) with one or more of the following characteristics:

- a. Fluid pH ≤ 7.20 or visually contains pus
 - b. Pleural fluid glucose ≤ 3.4 mmol/L
 - c. Positive bacterial or mycobacterial culture
 - d. Positive gram stain or stain for acid-fast bacilli
2. Clinical team expect to be able to perform a medical thoracoscopy, if allocated, on either the same or the next day as the effusion is diagnosed as requiring drainage
 3. Clinical team expect to be able to deliver the post-procedure trial schedule as detailed in the protocol

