7.1.2 Primary outcome analysis

The primary outcome (feasibility) will be assessed in three parts:

- The ability to recruit to the study will be determined by the proportion of the total number of “pre-screened” patients (those with suspected pleural infection seen during the trial period) who are not eligible for trial entry. The primary outcome will be defined as successful if <2/3 of pleural infection patients are recorded as pre-screen failures. This will be a surrogate for whether the trial’s question is applicable to a reasonable proportion of the pleural infection population.
- The ability to randomise patients to the trial interventions will be determined by the proportion of the total number of patients who are offered a patient information sheet (screened patients) who do not proceed to trial enrolment and randomisation. The primary outcome will be defined as successful if <2/3 of those who receive trial information are recorded as screen failures. This will be a surrogate for whether suitable patients are willing to take part in the trial, and whether any delays associated with trial recruitment impact on patient care.
- The ability to deliver the trial protocol will be determined by the proportion of the total number of patients who do not receive their allocated procedure on either the same day as randomisation or the next. The primary outcome will be defined as successful if <50% are recorded as allocation failures in both trial arms, assessed individually. This will be a surrogate for whether the trial centres are able to offer a rapid pleural intervention having committed to doing so.

Trial logs will also be scrutinised for specific reasons which occur regularly for pre-screen, screen, or allocation failures.

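### The pre-screen success rule is worded for pleural infection patients but counted over all suspected cases, so patients whose fluid meets no infection criterion can push it to failure

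*Protocol*

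**What the plan says.** Protocol section 7.1.2 judges feasibility in three parts. The first part uses three descriptions of its population in consecutive sentences.

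- The measure is given as: "proportion of the total number of “pre-screened” patients (those with suspected pleural infection seen during the trial period) who are not eligible for trial entry".
- Next comes the threshold: "The primary outcome will be defined as successful if <2/3 of pleural infection patients are recorded as pre-screen failures".
- The result is then to be read as a "surrogate for whether the trial’s question is applicable to a reasonable proportion of the pleural infection population".

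Section 5.1.1 says who enters the log: "All patients who have a suspected infected pleural effusion, based on radiological findings and routine clinical assessment by an appropriate specialist". No fluid result is required. It also says who counts as a failure: "Those who are ineligible for trial entry should have the reasons for this entered on the log, and will be deemed to be “pre-screen failures".

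Section 5.2, inclusion criterion 1, uses the same term with a different content: "Suspected pleural infection, defined as an effusion (in the appropriate clinical context) with one or more of the following characteristics". The list that follows is fluid-based: low pH or visible pus, low glucose, a positive culture, or a positive stain.

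Section 4.3.1 describes the outcome as counts of failures and "the proportions of each compared to the overall number assessed for trial involvement", which agrees with the broad denominator. Section 7.1.2 adds that the logs will be examined for recurring reasons for failure, but this does not enter the success rule.

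**The concern.** Suspected pleural infection has two meanings in the protocol. In section 5.1.1 it is a judgement from imaging and clinical assessment. In section 5.2 it needs at least one fluid finding. A patient who satisfies the first and, once sampled, not the second enters both the numerator and the denominator of the pre-screen proportion. No section takes such patients out again.

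The rule's stated purpose is to learn whether the trial's question fits a reasonable share of people with pleural infection. Patients whose fluid shows none of the defining features carry no information on that. The more of them there are, the harder the criterion becomes to meet, even if eligibility among the remaining patients is exactly as hoped. One of the three feasibility criteria could then be declared failed, and a larger trial discouraged, because suspicion was cast widely and not because the intervention suits too few infected patients.

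**Working it through.** **The plan's own figure.** Section 7.1.1 expects about 150 patients a year and accrual of one in five: 150 × 1/5 = 30, which reproduces the target. This is a planning number and does not enter the success rule.

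**Inputs.**
- Success threshold: recorded failures below 2/3 (section 7.1.2).
- u: share of pre-screened patients whose sampled fluid meets none of the inclusion criterion 1 findings. The protocol does not give it, so a range is assumed.
- f: failure proportion among all other pre-screened patients. Also not given; 50% and 60% are used because both satisfy the rule when u = 0.

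**Recorded proportion.** Every patient in the share u is a failure, so

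recorded failures = u + (1 − u)f.

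The rule is met only if u + (1 − u)f < 2/3, that is, if f < (2/3 − u)/(1 − u). For a given f, it fails once u reaches (2/3 − f)/(1 − f).

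| u (assumed) | Recorded, f = 50% | Recorded, f = 60% | f must be below |
|---|---|---|---|
| 0 | 50% | 60% | 66.7% |
| 10% | 55% | 64% | 63.0% |
| 16.7% | 58.3% | 66.7% (fail) | 60.0% |
| 20% | 60% | 68% (fail) | 58.3% |
| 33.3% | 66.7% (fail) | 73.3% (fail) | 50.0% |
| 50% | 75% (fail) | 80% (fail) | 33.3% |

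At u of 2/3 or more, no value of f passes.

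**Tipping points.**
- f = 60%: (0.6667 − 0.60)/(1 − 0.60) = 0.167.
- f = 50%: (0.6667 − 0.50)/(1 − 0.50) = 0.333.

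**The same in counts, for illustration.**
- Take 150 logged patients of whom 90 are ineligible (60%, a pass). Add 30 whose fluid meets no criterion: (90 + 30)/(150 + 30) = 120/180 = 66.7%, which is not below 2/3.
- Starting from 75 ineligible of 150 (50%), adding 75 gives 150/225 = 66.7%, again a fail.

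In both cases the result for the first 150 patients is unchanged; only the verdict differs.

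**The case against.** The best defence is that the operative denominator is stated and can be computed. The sentence before the threshold defines it as all pre-screened patients, and sections 4.3.1 and 5.1.1 agree. On that reading, pleural infection patients is shorthand for the group just named. Yield among all suspected cases is also a legitimate feasibility measure, and section 4.5 wants a full picture of the source population. Finally, the added patients can only make feasibility look worse, and the logged reasons allow the split to be reconstructed.

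Much of this stands. The rule is computable, the distortion runs only toward failure, and the data to undo it should exist. It does not answer the main point. The shorthand reading repairs the threshold sentence but not the next one, which gives the purpose as applicability to the pleural infection population. Examining reasons afterwards is descriptive and leaves the pass or fail verdict as it was.

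Some stronger readings are tempting but not supported:

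- A reader might infer that one site could succeed and another fail with the same eligible patients. The threshold is applied once, to the trial total; no site-level rule exists.
- A reader might take the introduction's statement about parapneumonic effusions, "around 10% of these go on to develop evidence of secondary infection", as implying about 90% failures. That figure concerns all reactive effusions after pneumonia. Section 5.1.1 logs only effusions that a specialist suspects are infected, on imaging and clinical assessment together.
- A reader might call the extra patients proven uninfected. The protocol supports only that they do not meet inclusion criterion 1; it labels even the group that does as suspected.
- A reader might see the 150 a year as a contradiction, since it comes from patients needing drainage. It plays no part in the rule.

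**Conclusion.** The concern holds. The first success criterion is worded and interpreted for one population and counted over a broader one, so followed as written it can return a failure unrelated to its stated purpose. If 60% of the remaining patients are ineligible, the verdict reverses once one logged patient in six has sampled fluid meeting no criterion; if 50% are, once one in three has.

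This shows that the verdict can reverse, not that it will. Neither u nor f is in the protocol, and at u = 10% both illustrative cases still pass. The documents do not support any claim about the likely size of u, nor any risk of false success from this source.

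**What to change.** In section 7.1.2, part 1, apply the <2/3 rule to pre-screened patients excluding those whose sampled fluid met none of the inclusion criterion 1 findings, and match the wording in section 4.3.1. The first part then reduces to f < 2/3 whatever u is.

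Keep patients whose fluid was never sampled in the denominator. Some may be infected but unsampled, for example because the effusion is too shallow or sepsis too severe (exclusion criteria 4 and 5 in section 5.3). They are ineligible, so dropping them would lower the failure proportion and favour success. Add a sensitivity analysis that excludes them. Report the proportion over all pre-screened patients alongside, as a descriptive figure, so that the full picture of the source population is kept.

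Section 5.1.1 already requires reasons for ineligibility on the log. The entry must distinguish fluid sampled with no criterion met from fluid not sampled. The threshold is already phrased for pleural infection patients, so the figure of 2/3 can stay. The cost is a somewhat smaller denominator, one extra reported line and the sensitivity analysis.

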5.1.2 Screening

Those who meet the trial inclusion and exclusion criteria should be entered onto the screening log and offered a patient information sheet (“screened patients.”). Those patients who do not proceed to trial enrolment should be recorded as “screen failures,” with the reason for this documented on the screening log. If a patient deteriorates clinically while they are considering trial entry such that they require urgent chest drainage before they are enrolled, they should also be recorded as a screen failure.

As per the inclusion criteria below, patients must undergo drainage on either the same or next day as they are diagnosed as needing drainage. Therefore, if a patient wishes to consider trial entry overnight, the trial team must be able to perform the allocated procedure on the *same* day as enrolment and randomisation.

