6.3 POST-RANDOMISATION

6.3.1 Control arm

Patients who are allocated to the control arm should undergo chest drain insertion on either the same or following day as they are *diagnosed as needing drainage*. Separate procedural consent must be taken as per local policy. Thoracic ultrasound guidance (either direct vision or contemporaneous marking) should be used for all such procedures. The chest drain may be inserted using either Seldinger or dissection techniques as per local hospital guidelines. It must be of size 16 French or greater and must be secured using at least one skin suture. The drain should be attached to an underwater seal (or digital equivalent), with the rate of initial fluid removal at the discretion of the inserting physician.

Following insertion, samples of pleural fluid should be taken directly from the drain and sent as per section 6.4.2 below. A post-procedure chest radiograph should be performed within 12 hours of drain insertion.

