6.3.2 Intervention arm

Patients who are allocated to the intervention arm should undergo a medical thoracoscopy on either the same or following day as they are *diagnosed as needing drainage*. Separate procedural consent must be taken as per local policy. Patients with a small effusion may have an induced pneumothorax performed prior to their thoracoscopy if necessary. The medical thoracoscopy should be performed as per local hospital guidelines, including using thoracic ultrasound where appropriate. Either a rigid or semi-rigid approach is acceptable, as are either single- or dual-port techniques. Conscious sedation may be used at the discretion of the operator. A sample of the pleural fluid which is drained should be sent as per section 6.4.2 below. During the procedure, the patient should undergo breakdown of accessible septations; parietal pleural biopsies; and intrapleural washout. Further details about these interventions may be found in the trial manual. At the end of the procedure, an appropriately-sized chest drain (minimum gauge 16 French) should be inserted and secured to the skin using at least one suture. The drain should be attached to an underwater seal (or digital equivalent) to allow full evacuation of the pleural cavity.

A post-procedure chest radiograph should be performed within 12 hours of completion of the thoracoscopy.

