6.3.3 Allocation failures

The nature of a participant's care is at all times the responsibility of the treating physician. However, on any occasion where treatment differs from that specified in the trial protocol then a protocol deviation form should be completed. In addition, patients who do not undergo their allocated procedure will be recorded as "allocation failures." The full reasons for all allocation failures should be recorded.

In the control arm, an allocation failure will refer to any patient who does not have a chest drain performed within the stipulated time window, or does not have a chest drain insertion performed as allocated.

In the intervention arm, an allocation failure will refer to any patient who does not have a medical thoracoscopy within the stipulated time window. Such patients should, in the first instance, aim to have a 16F gauge (or larger) chest drain performed as per the control arm.

If a patient is unable to undergo their allocated procedure, all subsequent tests and follow-up visits should be timed from the day of randomisation.

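### Allocation failure, one of the three parts of the primary outcome, is timed from diagnosis where it is defined and from randomisation where it is analysed

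*Protocol*

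**What the plan says.** Section 4.3.1 makes the number of allocation failures in both arms part of the primary outcome and refers to section 6.3.3 for the definition. Section 6.3.3 counts, in the control arm, "any patient who does not have a chest drain performed within the stipulated time window" (or whose drain insertion is not done as allocated) and, in the intervention arm, "any patient who does not have a medical thoracoscopy within the stipulated time window". It does not restate the window.

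The window is set elsewhere, always from the same starting point:

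- Section 6.3.2: intervention patients "should undergo a medical thoracoscopy on either the same or following day as they are" found to need drainage. Section 6.3.1 says the same of chest drain insertion in the control arm. Both sections put the reference to diagnosis in emphasis.
- Section 5.1.2: "patients must undergo drainage on either the same or next day as they are diagnosed as needing drainage".
- Section 5.2, inclusion criterion 2: the team must expect to be able to perform a thoracoscopy "on either the same or the next day as the effusion is diagnosed as requiring drainage".
- Appendix 2: both procedures are timed from the day the need for drainage is identified.

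Section 7.1.2, third part, changes the starting point. It assesses delivery of the protocol by the proportion of patients who "do not receive their allocated procedure on either the same day as randomisation or the next". Its next sentence calls these patients allocation failures and requires fewer than 50% in each arm, judged separately.

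**The concern.** One term has two clocks, and nothing in the protocol says which governs the primary outcome. The clocks agree when randomisation falls on the day of diagnosis. They can part when it falls a day later, and section 5.1.2 provides for that case by letting a patient consider entry overnight. It then requires the team to be able to treat on the day of randomisation itself, whereas 7.1.2 allows that same patient one further day.

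A patient treated on that further day is outside the window of 6.3.1 or 6.3.2, so 6.3.3 calls for a protocol deviation form. Yet 7.1.2 would count the patient towards successful delivery of the protocol.

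Section 2.2.1 says a larger trial must wait until urgent or semi-urgent thoracoscopy is shown to be possible within current services, and this criterion is the measure of that. If the analysis follows the looser wording, the failure rate may be understated. The thoracoscopy arm is probably the more exposed, since sections 4.5 and 9.7 expect difficulty in arranging urgent thoracoscopy. That is an inference; the protocol gives no delay rates.

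**Working it through.** **Inputs.** Section 7.1.1: about 150 patients a year and accrual of one in five. Section 4.2: 30 patients, 1:1. Section 7.1.2: success if under 50% are failures, each arm separately.

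**The plan's own figure.** 150 × 1/5 = 30, as stated. An even split gives 30/2 = 15 per arm; an exact 15/15 split is an assumption, because allocation is by minimisation with a random element.

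**The two clocks.** Let diagnosis be day 0, randomisation day r and the procedure day p, with p ≥ r.

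- Diagnosis clock (6.3.1 to 6.3.3): failure if p > 1.
- Randomisation clock (7.1.2): failure if p > r + 1.
- The clocks disagree when 1 < p ≤ r + 1. For r = 0 this is impossible. For r = 1 it means p = 2.

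| Randomised | Procedure | Diagnosis clock | Randomisation clock |
|---|---|---|---|
| day 0 | day 0 | success | success |
| day 0 | day 1 | success | success |
| day 0 | day 2 | failure | failure |
| day 0 | day 3 | failure | failure |
| day 1 | day 1 | success | success |
| **day 1** | **day 2** | **failure** | **success** |
| day 1 | day 3 | failure | failure |

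One of the seven timings is discordant. The opposite disagreement would need p > r + 1 with p ≤ 1, so r < 0, that is, randomisation before diagnosis. The 7.1.2 wording can therefore only lower the count.

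**Effect on the verdict.** One patient is 1/15 = 6.7 percentage points. The largest passing count is 7, since 7/15 = 46.7% and 8/15 = 53.3%. An arm with 7 failures on the randomisation clock and one discordant patient passes on that clock and fails on the other.

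A constructed example with a wider gap (assumed counts): 4 clear failures and 5 discordant patients give 4/15 = 27% on the randomisation clock and (4 + 5)/15 = 60% on the diagnosis clock.

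**Range.** The protocol gives neither the failure rate nor the discordant share, so both are assumed here. Let f be the failure rate on the randomisation clock and q the additional discordant share. An arm passes with probability P(X ≤ 7), where X is binomial with n = 15 and rate f on the randomisation clock or f + q on the diagnosis clock. Failures on the first clock are a subset of those on the second, so the probability that the verdicts differ is the difference between the two.

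| f | q | Pass, randomisation clock | Pass, diagnosis clock | Verdicts differ |
|---|---|---|---|---|
| 10% | 10% | 1.000 | 0.996 | 0.004 |
| 20% | 20% | 0.996 | 0.787 | 0.209 |
| 30% | 10% | 0.950 | 0.787 | 0.163 |
| 30% | 20% | 0.950 | 0.500 | 0.450 |
| 30% | 30% | 0.950 | 0.213 | 0.737 |
| 40% | 30% | 0.787 | 0.050 | 0.737 |

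Over f from 10% to 40% and q from 10% to 30%, the probability of opposite verdicts in an arm runs from 0.4% to 74%.

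**The case against.** The strongest reply is that 7.1.2 need not be read as a second rule. Its randomisation wording stands in the sentence that describes the proportion. The threshold sentence refers to patients recorded as allocation failures, which is the status assigned under 6.3.3. On that reading the pass/fail rule already uses the definition, and only the descriptive sentence is out of line. The reading is possible, but an analyst who follows the text of 7.1.2 would compute the other figure, and the protocol does not say which to use.

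It can also be said that randomisation was the intended start, because 7.1.2 describes the criterion as testing whether centres deliver once they have committed themselves. That is a sensible quantity, but it is not presented as a separate measure; it carries a term whose definition 4.3.1 places in 6.3.3. It is true that 6.3.3 reaches the diagnosis clock only by reference, but the only windows set for each arm are those in 6.3.1 and 6.3.2.

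Two further points stand as limits:

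- The affected group is narrow. The patient must have been randomised the day after diagnosis and then also have missed the procedure that day, which 5.1.2 and inclusion criterion 2 are meant to prevent. The upper end of the range above needs a large discordant share.
- The arms are judged separately, and reasons for every failure are recorded. No between-arm comparison is distorted by this, and the recorded dates and deviation forms may show late procedures.

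Neither removes the contradiction.

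**Conclusion.** The point holds. The protocol fixes one part of its primary outcome twice, with different starting points. For a patient randomised the day after diagnosis and treated the day after that, the two versions give opposite answers, and 7.1.2 is always the more lenient. At about 15 patients per arm, a single such patient is enough to change an arm's verdict if the count lies at the limit. The likely size is unknown: it may be negligible if overnight decisions are rare or are followed by same-day treatment. The conclusion rests on an even split, on timing counted in whole days, and on reading the window in 6.3.3 as the one set in 6.3.1 and 6.3.2. It should be corrected because it is a primary success criterion and the choice of clock would otherwise be open when the results are known.

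**What to change.** Reconcile the passages so that one clock scores the endpoint throughout, and settle it before the data are examined. The smallest change is one sentence in section 7.1.2: allocation failure is scored as defined in 6.3.3, using the windows in 6.3.1 and 6.3.2. A cross-reference to those sections in 6.3.3 would remove the remaining doubt about which window is meant. Time from randomisation to procedure can be reported beside it as a descriptive measure, which keeps the information on how centres perform once a patient is allocated. This concerns only how the endpoint is counted; it takes no position on which treatment window is clinically right.

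The cost is small. The reported failure rate may be somewhat higher than under the present 7.1.2 wording. The baseline list in section 6.1.2 does not name the date on which drainage was diagnosed as needed, so check that the eCRF or screening log holds it for every randomised patient, and add it if not.
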